2. Attach electrodes (so they're visible in the baseline video for optimal blinding).
3. Check resistance through electrodes. If $< 100 \Omega$, look for a short and correct it. If resistance remains out of range, do not proceed without specific approval from PI. Record resistance.
4. Optional but recommended bathroom stop
5. Procedures below are performed in a quiet room with only participant and study staff present but not conversing
6. All videos are recorded from the elbows up for later blinded ratings of tics
7. 5-min video-recorded baseline session, also rated live at the first visit to record baseline tic

frequency

8. At this point, the PI or designate will review the inclusion and exclusion criteria (including mean baseline tic frequency $\geq 1/\text{min.}$) and document eligibility for the study before additional procedures
9. Determine stimulation threshold for a train of 8 pulses (12 Hz, pulse width 200 μs), starting at 1mA and increasing until a twitch of the thumb is seen, to a maximum of 20mA (expected range 2-15 mA, *personal communication, [name] to [name]*). Some subjects may wish to withdraw at this point if suprathreshold stimulation is too uncomfortable, but in the Nottingham report, participants age 15 and up found the stimulation tolerable. Since electrode placement can change slightly between visits, on the second visit the threshold is verified and adjusted as needed. We record the threshold at each visit.
10. Resume video recording
11. Synchronize clocks for video, urge rating software, and stimulation
12. MNS stimulation on or off blocks as follows, without planned breaks (total 29-44 min.)
 - a. Two 1-min. blocks of MNS on and two 1-min. sessions off, the order of these 4 sessions randomized (*this design matches the Nottingham study*)
 - b. 5-min. block MNS off
 - c. 5-min. block MNS on
 - d. 5-min. block MNS off
 - e. 5-min. block MNS on
 - f. 5-minute stimulation **off** blocks until tics return to baseline frequency (min. 1 block, max. 4 blocks)
13. Stop video recording
14. CGI-I (Clinical Global Impression of Improvement) rating for tics by participant and investigator
15. Debrief
 - a. ratings of tic improvement and discomfort using the CGI Efficacy Index
 - b. ask for comments on benefit, tolerability, side effects
 - c. participant and staff guess whether this was active or control stimulation day (*to test adequacy of blinding*)
 - d. ask if they think they would use a portable stimulator

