An expert rater blind to condition and time point assesses the number of tics per minute. Change in tic frequency from baseline (stimulation off) is compared between 5-minute MNS-on epochs on the rhythmic vs. the arrhythmic day. Subjects who do not complete both stimulation visits will not be included in this analysis. A repeated measures ANOVA will be used to compare effects of visit, order (rhythmic day first or second) and stimulation (on vs. off) on tic frequency. The hypothesized change is a significant interaction of visit, order and stimulation factors ($p \leq 0.05$),

showing greater improvement (off to on) with rhythmic vs. arrhythmic stimulation. This analysis includes the first six 5-minute blocks on each MNS day (i.e., the blocks that all participants complete).

[Time Frame: During rhythmic MNS stimulation]

4. Change in tic severity during rhythmic MNS (vs. arrhythmic MNS)

Overall tic severity for each 5-minute block is rated once on a 5-point scale by an expert blind to condition and time point. The scale is the Intensity item from the Yale Global Tic Severity Scale [YGTSS], which uses integer scores from 0 (no tics) to 5 (severe intensity). For this analysis, we will define tic severity as $\max\{\text{phonic tic intensity score, motor tic intensity score}\}$. Change in tic severity from baseline (stimulation off) is compared between 5-minute MNS-on epochs on the rhythmic vs. the arrhythmic day. Subjects who do not complete both stimulation visits will not be included in this analysis. A repeated measures ANOVA will be used to compare effects of visit, order (rhythmic day first or second) and stimulation (on vs. off) on tic frequency and severity. The hypothesized change is a significant interaction of visit, order and stimulation factors ($p\le.05$), showing greater improvement (off to on) with rhythmic vs. arrhythmic stimulation. This analysis includes the first six 5-minute blocks on each MNS day (i.e., the blocks that all participants complete).

[Time Frame: During rhythmic MNS stimulation]

Secondary Outcome Measures:

5. Change in tic severity after MNS ends

Duration of benefit will be estimated as follows. A repeated measures ANOVA will compare the change in tic frequency from baseline, during each 1-minute-long period following the end of stimulation. Here baseline means the tic frequency during the last 5 minutes of MNS from the same day.

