[Time Frame: up to 20 minutes after the end of stimulation at each study visit up to 1 month]

6. CGI-I, participant

Clinical Global Impression of Improvement (CGI-I), rated by participant. The CGI-I is a 7-point scale ranging from 1 = very much improved to 7 = very much worse.

[Time Frame: 5-25 minutes after the end of stimulation at each study visit up to 1 month]

7. CGI-I, investigator

Clinical Global Impression of Improvement (CGI-I), rated by investigator.

[Time Frame: 5-25 minutes after the end of stimulation at each study visit up to 1 month]

8. VAS rating of premonitory urge severity

Participant rates the maximal severity of any premonitory urges over the preceding minute, from 0=no premonitory urge to 100=maximally uncomfortable premonitory urge, using a Visual Analog Scale.

[Time Frame: Before MNS begins and at the end of each 5-min. MNS on or off block, at each study visit up to 1 month]

9. Rating of therapeutic effect using the CGI Efficacy Index

Participant rates peak improvement experienced during the visit using the 4-point scale of the CGI (Unchanged or worse; Minimal - Slight improvement that doesn't decrease the overall impact of

symptoms*; Moderate - Decided improvement. Partial remission of symptoms; Marked - Vast improvement. Complete or nearly complete remission of all symptoms). * = "Minimal" option anchor text slightly edited from original

[Time Frame: 5-25 minutes after the end of stimulation at each study visit up to 1 month]

10. Rating of discomfort using the CGI Efficacy Index (edited)

Participant rates peak discomfort experienced during the visit using the 4-point scale of the CGI:

"Overall, today, how much DISCOMFORT did the stimulation cause? If discomfort is the wrong word, please substitute any negative effects or side effects of stimulation. (No discomfort; Discomfort noticeable, but not severe enough to concern me or to turn it off; Enough discomfort, impairment of functioning or social embarrassment that I would only keep it on if the benefit was considerable; Caused discomfort, impairment of functioning or social embarrassment to a degree that any treatment benefit was not worth leaving it on).

[Time Frame: 5-25 minutes after the end of stimulation at each study visit up to 1 month]

11. Blindedness assessment

Participants guess whether they received the active or sham MNS condition, and rate their certainty for that guess on a 0-3 scale (0 = pure guess, 3 = certain).

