severity. The hypothesized change is a significant interaction of visit, order and stimulation factors ($p \leq .05$), showing greater improvement (off to on) with rhythmic *vs.* arrhythmic stimulation. The primary analysis will focus on the first six 5-minute blocks (*i.e.*, the ones that all participants complete). A secondary analysis examines the last 40 s of the four 1-minute blocks in the same way. Paired t tests will compare CGI-I ratings between stimulation conditions (rhythmic *vs.* arrhythmic).

Aim 2 interpretation: We chose arrhythmic stimulation as the control condition (“placebo”) because it did not increase stimulation-frequency EEG power in the sensorimotor cortex. However, we note that arrhythmic stimulation may itself possibly confer active benefit, which may produce a non-significant result for Aim 2. In that case a different control condition may be required for subsequent study, such as sub-motor-threshold stimulation current or a wait list condition. Additionally, this pilot study will not address the specificity of the stimulation site—as stimulation of another peripheral nerve may prove equally effective—nor the specificity of the 10-12 Hz stimulation frequency. Finally, other modifications may provide greater benefit; *e.g.* bilateral stimulation may be more effective than unilateral. All of these possibilities are reasonable goals of future study, but this pilot study focuses on the methods used in the published work.

Aim 3. The duration of benefit analysis will use a repeated measures ANOVA for tic scores from each 1-minute segment after the end of stimulation. A secondary approach may be to fit the tic scores from each participant after the end of each stimulation block to an exponential decay model. The analysis of individual characteristics that predict improvement with simulation will use a 2-tailed t test or correlation, as appropriate, for each measured demographic and clinical feature. These will include age, sex, baseline YGTSS, baseline OCD severity rating, baseline ADHD severity rating, history of complex tic(s), history of phonic tic(s), and motor and phonic tic frequency and severity at baseline (blinded ratings of the 5-minute block before stimulation on the first study visit). Other outcome variables, such as discomfort, adequacy of blinding, and interest in a portable stimulator, will be summarized descriptively.

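### The duration-of-benefit ANOVA covers each minute up to 20 after stimulation, but minutes 6–20 are recorded only for participants judged not yet back at baseline

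*Combined protocol and SAP*

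**What the plan says.** **Data collected.** Stimulation protocol, step 12f, closes each session with 5-minute off "blocks until tics return to baseline frequency (min. 1 block, max. 4 blocks"). The whole sequence runs "without planned breaks (total 29-44 min"), so its length differs between participants.

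**Analysis.** Under Data analysis, Aim 3: "The duration of benefit analysis will use a repeated measures ANOVA for tic scores from each 1-minute segment after the end of stimulation". Secondary Outcome 5 describes the same method, applied to change from baseline "during each 1-minute-long period following the end of stimulation", with a time frame of "up to 20 minutes after the end of stimulation".

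**Baseline.** Secondary Outcome 5 adds: "Here baseline means the tic frequency during the last 5 minutes of MNS from the same day". Step 12f does not define its own baseline frequency. The natural reading is step 7, the "5-min video-recorded baseline session, also rated live at the first visit", which comes before any stimulation.

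**Limit used elsewhere.** For Aim 2 the primary analysis is confined to the first six 5-minute blocks, described as "the ones that all participants complete". Aim 3 and Secondary Outcome 5 carry no such limit and no rule for unrecorded minutes.

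**The concern.** Whether a participant contributes minutes 6–20 depends on the outcome under study. Those whose tics return quickly leave the recording and those who return slowly stay. A minute-by-minute comparison out to 20 minutes therefore does not describe the cohort that was stimulated.

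The protocol's objectives treat the duration of effect as central to designing chronic treatment. A reader of the planned result could not tell whether the reported duration was too long or too short. The only caution promised for Aim 3 is about multiplicity, which does not address selection.

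**Working it through.** **1. Recording length.** Steps 12a–12e take 4 × 1 + 4 × 5 = 24 min. One to four further 5-minute blocks give 24 + 5 = 29 and 24 + 20 = 44 min. This matches the plan's 29–44 min, so post-stimulation recording lasts 5 to 20 minutes.

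**2. Who is recorded.** The six blocks that everyone completes are the step 7 baseline, 12b to 12e, and the first block of 12f (1 + 4 + 1 = 6).

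| Minutes after last stimulation | Recorded for |
|---|---|
| 1–5 | everyone |
| 6–10 | those not judged back after block 1 |
| 11–15 | those not back after blocks 1 and 2 |
| 16–20 | those not back after blocks 1, 2 and 3 |

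Step 12d, the off block after the first 5-minute on block, is also complete for everyone.

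**3. Effect of the method.** A classical repeated measures ANOVA needs a value in every cell. Over 20 minutes it keeps only the last row of the table, and those participants' minutes 1–15 are then analysed too. Using whatever exists in each minute instead means that the group changes from block to block.

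**4. Illustrative size.** Assumptions, not from the documents: mean 10 tics/min, between-person log-SD 0.6, average reduction 30% during stimulation, and recording stopped when a block reaches 100% of the same-day pre-stimulation count. The measure is the ratio of the post-stimulation rate to the stimulation-on rate, which is the plan's own contrast. A ratio read too low makes benefit look longer-lasting; one read too high makes it look shorter.

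True ratio with no after-effect: 1/(1 − 0.30) = 1.43 in every block. With a 5-minute half-life, the average fraction of benefit left in block 1 is (1 − 0.5)/ln 2 = 0.721, so the ratio is (1 − 0.30 × 0.721)/0.70 = 1.12. The fraction halves with each block, which gives 1.27, 1.35 and 1.39.

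| Scenario | True, blocks 1–4 | Complete rows |
|---|---|---|
| Uniform response, no after-effect, Poisson noise | 1.43 throughout | 1.36 / 1.36 / 1.36 / 1.43 |
| Same, with 25% block variation | 1.43 throughout | 1.28 / 1.28 / 1.28 / 1.43 |
| 40% non-responders, 50% reduction in the rest, half-life 5 min, Poisson noise | 1.12 / 1.27 / 1.35 / 1.39 | 1.17 / 1.39 / 1.47 / 1.60 |

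In the first two rows a flat truth becomes a false late rise, and in the third the error has the opposite sign. In the third, available-case means read 1.12 / 1.39 / 1.54 / 1.60, so keeping every recorded minute does not remove the problem when response varies.

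A second simulation (log-SD 0.5, decay constant 5 min) agrees on direction. It gives the rise above the stimulation-on level in blocks 1–3, in tics/min, with a stop at 100%:

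- Decay time varies: 1.20 / 2.14 / 2.48 in the full cohort against 0.92 / 1.66 / 1.95 in complete rows.
- Benefit varies: 1.10 / 2.30 / 2.74 against 1.30 / 2.64 / 3.02.

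**5. Number with all 20 minutes, out of 32.** With a stop at 100%: 7 to 19 across the scenarios, of which 7–8 with no after-effect. The width of a 95% confidence interval at equal SD is proportional to t(0.975, n − 1)/√n. Relative to n = 32 it is 2.57 times as wide at n = 7 and 1.34 times at n = 19. With no after-effect and Poisson noise, the count falls from 7.4 to about 3 if recording stops at 90% of baseline, and to about 1 at 80%.

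**The case against.** Four points can be made on the other side.

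- **Dropping of incomplete rows is not in the plan.** This is correct. A reader might infer that the plan commits to estimating duration from a handful of slow returners. The documents do not say so: the 20 minutes is a maximum, no rule for empty cells is given, and 7–19 of 32 is not a handful. The overall statistical approach also refers to an analysis strategy registered before enrolment, which was not available here and may contain a rule. What remains is that the later minutes are selected on the outcome under either handling.
- **The exponential decay fit needs no common follow-up length.** This is true, and because it follows each stimulation block it can use step 12d. But the plan offers it only as something that may be done, after the ANOVA.
- **The numbers are assumed.** This stands in full. The plan gives no stopping threshold or counting method. At an 80% threshold the errors in the ratio reach −0.22 and +0.39, beyond the −0.16 to +0.21 seen at 100%. No simulated figure should be read as a property of the design.
- **Aim 3 is exploratory.** This is conceded and it limits the severity.

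A reader might also infer that the planned analysis must exaggerate how long benefit lasts. Against the plan's own reference level that does not follow, because the sign depends on how response and decay vary. The background section says that benefit was dramatic in some participants and outlasted stimulation in some, so variation is plausible.

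**Conclusion.** The point holds, and the analysis is wrong as written: it is specified for minutes that the protocol does not record for everyone, and which minutes are missing depends on the outcome. This follows from step 12f and the analysis text alone. The direction of the error is not known in advance. Its size depends on an unstated stopping threshold and on an unknown tic rate, decay time and spread of response.

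It should be fixed, but its reach is limited. The outcome is secondary, Aim 3 is labelled hypothesis-generating, minutes 1–5 are complete, and no primary outcome or safety matter is affected.

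**What to change.** 1. Limit the repeated measures ANOVA to minutes 1–5 after the last stimulation block. The step 12d off block can be analysed in the same way.
2. For minutes 6–20, do not compare minute means as if they came from the full cohort. Show the number recorded in each block, and report time to return to baseline in 5-minute intervals, censored at 20 minutes, by stimulation day. Note that some participants will count as not returned by chance, at a rate that depends on the stopping threshold. With no benefit at all, the second simulation still had 15.2 of 32 being recorded in minutes 6–10 with a stop at 100%, and 9.8 with a stop at 90%.
3. If later minutes are modelled, use a likelihood-based mixed model on all recorded blocks, including the same-day pre-stimulation block and the last stimulation-on block. State the missing-at-random assumption, which is reasonable only so far as the blinded counts reflect the live judgement that ended recording. In the simulations with mixed responders, a random-intercept version still read up to 0.10 too high.
4. Reconcile the baseline frequency in step 12f with the separate definition of baseline in Secondary Outcome 5.

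The cost is plan wording and a little extra analysis, with no change to visits or data collected. The downside is that less can be claimed about minutes 6–20.

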You may experience one or more of the risks indicated below from being in this study. In addition to these, there may be other unknown risks, or risks that we did not anticipate, associated with being in this study. You will be told of any new information that may affect your willingness to participate in this study. [name] will answer any questions you have about these risks.

MNS

Likely:

- Discomfort in the forearm, wrist or hand during active stimulation
- Mild skin irritation from applying or removing the surface electrodes

Other study procedures

Likely:

- The questionnaires and interview may be slightly boring, fatiguing or challenging.
- The video recordings may be slightly boring

Rare:

- The questions that you are asked during this study could make you feel uncomfortable. If any question makes you feel uncomfortable, you may choose not to answer it.
- Confidential information about you may be accidentally disclosed. However, we think the risk of accidental disclosure is small. The information we gather during the course of the study is coded only by a study number and is kept separately from your name, address, etc.

LOCATIONS / SITES OF STUDY

Data collection: Washington University in St. Louis

Data analysis: Washington University in St. Louis

STUDY DURATION

Anticipated duration of entire research activity per participant:

- 2-4* days, usually over the course of 1-2 weeks

* Planned participation includes a screening visit followed by two stimulation sessions, the first of which may occur on the same day as the first stimulation session. The maximum of 4 days rather than 3 allows one additional make-up MNS session for each participant in the event of technical problems that prevent completion of the procedures.

Anticipated duration of entire research activity:

One year

SAMPLE SIZE

N = 32 (study completers)

Power considerations

We can estimate variance from the Nottingham tic frequency results. Fig. 5 in ref. [6] shows the SD of the improvement in tic frequency between the MNS on and off conditions to be ~81 (total tics per condition). The mean difference between conditions was ~41, corresponding to a nearly 30% mean decrease in tic frequency. A 25% decrease in tic severity using the YGTSS Total Tic Score (TTS) is highly predictive of *clinically meaningful* clinical improvement [17], and the TTS is highly correlated to tic frequency on video recordings [18,19].

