From these data, a sample size of 32 will have 81% power to find a statistically significant result for Aim 1 (two tails) assuming the population mean response is the 30% reported by our colleagues in Nottingham. This sample size provides 75% power to detect clinically meaningful (-25%) improvement (one tailed).

Estimating screen failures and dropouts at a total rate of 27%, we will plan to enroll up to 44 participants to arrive at 32 who complete the entire study.

INCLUSION CRITERIA

Inclusion criteria for all subjects:

- Age 15-64 inclusive at initial screening visit
- Informed consent by adult subject; assent by child and informed consent by guardian
- Current DSM-5 Tourette's Disorder or Persistent (Chronic) Tic Disorder
- At least 1 tic per minute (average) during the first 5-min. baseline video session on the first visit (as scored during the session by the investigator)

EXCLUSION CRITERIA

Exclusion criteria for all subjects:

- Unable to complete study procedures for any reason
- Has an implanted device that could be affected by electrical current
- Pregnancy known to participant or (for children) to the parent
- Known or suspected primary genetic syndrome (e.g. Down syndrome, Fragile X)
- Intellectual disability (known, or likely from history and examination)
- Head trauma with loss of consciousness for more than 5 minutes
- Significant neurologic disease, not counting TS (exceptions include febrile seizures or uncomplicated migraine)
- Severe or unstable systemic illness
- Factors (such as exaggerated signs) that in the judgment of the principal investigator make the video recording or YGTSS an inaccurate assessment of tic severity
- Judged by investigator to be unlikely to complete study procedures or to return for later visits
- Change in somatic or psychotherapeutic treatment in the 2 weeks preceding the first stimulation visit
- Planned change in somatic or psychotherapeutic treatment between the 2 stimulation visits

CONCOMITANT MEDICATIONS

Required: none

PROHIBITED MEDICATIONS

none

TREATMENTS AND DOSAGE

Rhythmic

- 10 Hz for 1-minute epochs (to replicate **Current Biology** report)

- 12 Hz for 5-minute epochs

Arrhythmic

- Same number of pulses per minute as in the rhythmic condition, but with a random inter-pulse interval, as implemented by the Nottingham group in the **Current Biology** report

Both

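### Must Aim 3 say which measure of improvement its predictor analyses use?

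*Combined protocol and SAP*

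**What the plan says.** In the Data analysis section, Aim 3 gives the method for "individual characteristics that predict improvement with simulation will use a 2-tailed t test or correlation, as appropriate, for each measured demographic and clinical feature". The features are age, sex, baseline YGTSS, OCD rating, ADHD rating, and any past complex tics or (as a separate feature) past phonic tics. The last item in the list reads "motor and phonic tic frequency and severity at baseline (blinded ratings of the 5-minute block before stimulation on the first study visit". That makes 11 if the last item counts as four. The dependent variable is not defined.

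Elsewhere the word improvement appears in these ways:

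- Power considerations, as a raw difference: "the SD of the improvement in tic frequency between the MNS on and off conditions to be ~81 (total tics per condition".
- Power considerations, as a percentage: "75% power to detect clinically meaningful (-25%) improvement (one tailed".
- Data analysis, Aim 2, as a contrast in tic frequency and severity: "showing greater improvement (off to on) with rhythmic" stimulation than with arrhythmic.
- Secondary Outcome Measure 6: "Clinical Global Impression of Improvement (CGI-I), rated by participant". Measure 7 is the same scale rated by the investigator.
- Secondary Outcome Measure 9: "Participant rates peak improvement experienced during the visit using the 4-point scale of the CGI".

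Primary Outcome Measures 3 and 4 fix the blocks for Aim 2: "This analysis includes the first six 5-minute blocks on each MNS day (i.e., the blocks that all participants complete". The paragraph on the overall statistical approach calls Aim 3 mainly hypothesis-generating, promises a warning about multiple tests, and says that the hypotheses and analysis strategy were registered on OSF before enrolment. That registration is not among the documents.

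**The concern.** An analysis of predictors with no named outcome leaves the analyst free to choose one after seeing the data. Counting every use of the word gives up to six candidates: raw frequency, percentage frequency, severity, two CGI-I ratings and the Efficacy Index. The plan gives prevention of HARKing as its reason for registering, so the silence is awkward.

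The choice also matters for one listed predictor. If stimulation removes the same percentage of tics at every baseline, people with more tics lose more tics in absolute terms, while their percentage change is unrelated to baseline. A report that frequent tics predict more improvement would then be true on one scale and not on the other. Aim 3 is meant to inform a later efficacy trial, so a misread predictor could mislead its design.

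There is a second worry. If the six common 5-minute blocks define the change, the block recorded before stimulation at visit 1 is both the predictor and, for participants whose first day is rhythmic, one of the off blocks in the outcome. That builds in some correlation.

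**Working it through.** **1. The plan's own figures.** Inputs from the sample size section: mean difference about 41, SD about 81, n = 32. Alpha of 0.05 is assumed.

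- Aim 1: d = 41/81 = 0.506. The two-sided paired t test gives 79.2% and the normal approximation 81.7%, against 81% stated.
- 25% improvement: 41 × 25/30 = 34.2 tics, d = 34.2/81 = 0.422. The one-sided paired t test gives 75.5%, against 75% stated.
- Enrolment: 32/(1 − 0.27) = 43.8, so 44, as stated.

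The 75% reproduces when 25% is turned into raw tics and set against the raw SD. The percentage there re-expresses a group mean; it is not a percentage change computed for each participant.

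**2. How many rival outcomes remain.** The off-to-on change is a contrast that overlaps the raw difference, so it is not a separate candidate. The Aim 2 paragraph refers to the global ratings by the name of the scale, and Measure 9 is titled as a rating of therapeutic effect. Reading the Data analysis section straight through, improvement is the off-to-on change in tic frequency and severity. Day, blocks and scale stay open.

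**3. Can scale change the answer?** Yes. A fall from 4 to 2 tics/min is a drop of 2 (50%); a fall from 20 to 15 is a drop of 5 (25%). The second person improves more on the raw scale and less on the percentage scale.

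A simulation (3,000 trials per setting, n = 32, Pearson correlation, |r| of at least 0.349 needed for p < 0.05) assumed a mean of 10 tics/min, between-person CV of 0.5 to 1.2 and extra-Poisson variance of 0.02 or 0.10:

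| Assumed benefit | Mean r, raw | Mean r, percentage | Verdicts differ |
|---|---|---|---|
| 30% on average at every baseline (individual SD 0.30) | 0.20 to 0.48 | 0.01 to 0.02 | 30–74% |
| About 3 tics/min from everyone | 0.00 to 0.07 | −0.31 to −0.68 | 43–80% |

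The two rows reverse each other, so neither scale is the safe one. None of these inputs is in the documents.

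**4. Open choice of outcome.** With 11 independent null features and one outcome, 1 − 0.95^11 = 43% of trials show at least one p < 0.05. With six equally correlated outcomes (assumed correlation 0.3 to 0.9) and features correlated 0 to 0.5, the figure is 57–95%. That is the chance of any small p-value among 6 × 11 = 66 tests. If all are shown, it is what the multiplicity warning describes. It becomes bias only if results are selected.

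**5. The shared block.** Step 12 of the stimulation protocol lasts at least 4 × 1 + 4 × 5 + 5 = 29 minutes, as stated, and so holds five common 5-minute blocks. A sixth is reached only by counting the baseline in step 7. The off blocks are then step 7, 12b, 12d and the first 12f; the on blocks are 12c and 12e.

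Dropping step 7 would end the overlap. With independent block noise, variance goes from 1/4 + 1/2 = 0.75 to 1/3 + 1/2 = 0.833, so the SD rises by √(0.833/0.75) − 1 = 5%. Signal is lost too. Suppose a 30% benefit, half of it persisting into 12d and 12f:

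- With step 7: (1 + 1 + 0.85 + 0.85)/4 − 0.70 = 22.5%.
- Without: (1 + 0.85 + 0.85)/3 − 0.70 = 20.0%.
- If 12b is affected too: 18.8% with step 7 and 15.0% without.

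The loss is 11% to 20% of the measured change.

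**The case for a change.** The best case for a change is that it costs one sentence and closes a real gap. Nothing in the documents fixes the outcome. Appeal to the primary outcome does not settle it, because there are four: frequency and severity, each on 1-minute and on 5-minute blocks. The multiplicity warning speaks to the number of tests, not to choice among outcomes. The provision for transformation in the additional analysis details names none and rests on visual inspection.

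Much of this stands. The text is silent on day, blocks and scale, and scale matters for baseline frequency. The overlap of predictor and outcome is also real on the six-block reading.

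Three parts do not carry through. The list of six rivals ignores the gloss in the Aim 2 paragraph. The harm assumes a report that omits its units, since a correlation with change in tics/min and one with percentage change cannot be confused once labelled. The remedies gain little: showing both scales leaves the choice open, and log change needs a rule for zero counts. Removing step 7 discards the only off block recorded before any stimulation that day, although the Objectives hypothesise benefit that lasts beyond stimulation. That is a trade-off, not a correction.

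**Conclusion.** No change to the plan is called for. This is missing detail in an exploratory analysis, and an analyst can fill it sensibly: take the off-to-on change in tic frequency and severity, and state the day, blocks and scale with each result. No primary test, sample size or stated power figure is affected.

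The effect is confined to how the baseline-frequency predictors are read. There, absolute and relative change answer different questions and neither is wrong. The simulated rates of disagreement, 30–80% across both models, rest on assumed tic rates, spread and form of benefit. They show that disagreement is possible and should not be quoted as estimates for this trial. Keeping or dropping the pre-stimulation block is a fair choice either way, and the question arises only if the six-block change is used.

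The conclusion assumes that Aim 3 is reported as described, as hypothesis-generating and with its warning, and that results are not selected by p-value. The OSF registration may already define the variable; the conclusion does not depend on it.
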